3.5.6 Pharmacokinetics Per-Protocol Set

The Pharmacokinetic Per-Protocol Set (PK-PPS) will consist of all randomized subjects who received at least 1 dose of IMP and had at least 1 quantifiable post-dose plasma concentration.

3.5.7 Pharmacodynamics Per-Protocol Set

The Pharmacodynamic Per-Protocol Set (PD-PPS) will be a subset of the FAS, consisting of those subjects who had no IPDs potentially affecting the PD data, as confirmed during pre-analysis review of the data prior to database lock.

3.6 Treatment assignment and treatment groups

Listings and summaries will be presented by treatment group and for all subjects in the relevant analysis sets, where applicable. Treatment assignment is given in [Table 14–11](#).

The following order will be used in the TFLs (with the treatments displayed accordingly):

- Not randomized (if applicable)
- PBO
- ADA

- BKZ
- All subjects

The dosing schedules and number of injections given at each visit are described in [Table 3–2](#). Due to the differences in the dosing schedule between bimekizumab and adalimumab, placebo injections will be administered along with active drug such that all subjects will receive the same number of injections at each corresponding visit.

Table 3–2: Administration of investigational medicinal product

Visit	Treatment group		
	Adalimumab ^a (Total # injections, # of placebo injections)	Bimekizumab ^b (Total # injections, # of placebo injections)	Placebo
Baseline	160mg (4 active injections, no placebo injections)	640mg (4 active injections, no placebo injections)	4 placebo injections
Week 2	80mg (2 active injections, no placebo injections)	320mg (2 active injections, no placebo injections)	2 placebo injections
Weeks 4, 6, 8, and 10	40mg (1 active injection, 1 placebo injection)	320mg (2 active injections, no placebo injections)	2 placebo injections
Weeks 5, 7, and 9	40mg (1 active injection, no placebo injection)	NA (no active injection, 1 placebo injection)	1 placebo injection

NA=not applicable

^a Each individual adalimumab injection will be 40mg.

^b Each individual bimekizumab injection will be 160mg.

In the case of dosing administration errors during the Treatment Period, all statistical analyses of safety data will be conducted according to the actual treatment received, ie, treatment assignment for the SS will be based on actual treatment with the following rules:

- Subjects randomized to placebo who received at least 1 dose of bimekizumab will be summarized in the ‘BKZ’ treatment group
- Subjects randomized to bimekizumab who received placebo throughout the Treatment Period will be summarized in the ‘PBO’ treatment group
- Subjects randomized to bimekizumab who received any doses of placebo during the Treatment Period, but at least 1 dose of bimekizumab, will be summarized in the ‘BKZ’ treatment group
- Subjects randomized to bimekizumab who received any doses of adalimumab during the Treatment Period, but at least 1 dose of bimekizumab, will be assessed at the DEM for the treatment group assignment, as it will depend on how many doses of each of the treatments were taken and at what time point during the study

- Subjects randomized to placebo who received at least 1 dose of adalimumab will be summarized in the ‘ADA’ treatment group
- Subjects randomized to adalimumab who received placebo throughout the Treatment Period will be summarized in the ‘PBO’ treatment group
- Subjects randomized to adalimumab who received any doses of placebo during the Treatment Period, but at least 1 dose of adalimumab, will be summarized in the ‘ADA’ treatment group
- Subjects randomized to adalimumab who received any doses of bimekizumab during the Treatment Period, but at least 1 dose of adalimumab, will be assessed at the DEM for the treatment group assignment, as it will depend on how many doses of each of the treatments were taken and at what time point during the study
- Subjects randomized to placebo who received at least 1 dose of adalimumab and at least 1 dose bimekizumab will be assessed at the DEM for the treatment group assignment, as it will depend on how many doses of each of the active treatments were taken and at what time point during the study

Subjects receiving the incorrect treatment at a particular visit will be excluded from the PPS, PD-PPS and the PK-PPS as this would be considered as an IPD. Subjects may be excluded from the analysis at a particular visit (or visits) only or overall, following discussion at the DEMs, and will be included in the analyses according to their randomized treatment (which would be equivalent to an analysis according to their actual treatment)

All statistical analyses of the PK and immunological data will be conducted according to the actual treatment received, ie, treatment assignment for the PK-PPS will be based on actual treatment.

Similarly, all statistical analyses of the PD data will be conducted according to the actual treatment received, ie, treatment assignment for the PD-PPS will be based on actual treatment.

3.7 Center pooling strategy

The data from different sites will be pooled for all analyses. No stratification by site or country will be performed.

3.8 Coding dictionaries

Adverse events and medical history will be coded using the Medical Dictionary for Regulatory Activities (MedDRA®) version 19.0.

Medications will be coded according to the World Health Organization Drug Dictionary (WHODD) version SEP2015. Medical procedures will not be coded.

3.9 Changes to protocol-defined analyses

The following changes relative to the protocol-defined analyses have been included in the SAP:

- The protocol defines the HiSCR as “at least a 50% reduction from Baseline in the total abscess and inflammatory nodule count, with no increase from Baseline in abscess or draining fistula count”. The SAP defines this as “at least a 50% reduction from Baseline in the total abscess and inflammatory nodule count, with no increase from Baseline in abscess **or draining tunnels (fistulas/sinus tracts) count**”

- The section on the determination of the sample size in the protocol states that, with the planned sample size of 80 subjects, the probability of study success is 85%. Subsequent simulations have been performed and the probability found to be 99%. The SAP thus states this 99% probability in [Section 2.4](#) instead.
- The PD-PPS was included as an additional analysis set in the SAP and was not part of the clinical study protocol. This was added as it was deemed appropriate to review protocol deviations separately in relation to these data and to define a separate analysis set accordingly.
- The definition of the FAS was updated to include all subjects with a valid Baseline measurement and a post-Baseline measurement for at least 1 efficacy variable. In the protocol, the definition included only subjects with a valid Baseline measurement and a post-Baseline measurement for the primary efficacy variable. Since the primary efficacy variable is a composite endpoint based on abscess count, inflammatory nodule count and draining tunnel (fistula/sinus tract) count, using this definition, any subjects with at least 1 missing component of the composite endpoint would not be included in any of the efficacy analyses.
- Based on the second interim analysis for this study, additional exploratory efficacy variables based on the lesion count assessment data, HiSCR depth and disease flare status, have been defined in this SAP amendment. [Section 8.2.4](#) includes details on the derivation of different HiSCR depths and [Section 8.2.5](#) describes the planned summaries of this additional variable. [Section 8.3.1.2](#) defines disease flare and includes details on planned summaries of disease flare status and the number of visits at which a subject experienced a disease flare during the Treatment Period.

4 STATISTICAL/ANALYTICAL ISSUES

4.1 Adjustments for covariates

Randomization will be stratified by Baseline Hurley Stage in this study. Accordingly, all statistical models fitted in the analyses of the primary efficacy variable will include the stratification factor for Baseline Hurley Stage as a covariate.

In cases of classification errors at the time of randomization, subjects may be assigned to an incorrect stratum. In these cases, subjects will be included in the statistical modelling according to the observed values of Baseline Hurley Stage regardless of the value used by the site to stratify the subject at randomization.

Concomitant antibiotic use at entry into the study will be included as an additional covariate in the supportive and sensitivity analyses of the primary efficacy variable.

4.2 Handling of dropouts or missing data

4.2.1 Efficacy data

There will be no imputation of missing data for the individual components of the HiSCR (abscess count, inflammatory nodule count and draining tunnel (fistula/sinus tract) count).

For subjects with a missing HiSCR due to missing component data at a specific visit, or due to early discontinuation from the study during the Treatment Period, non-responder imputation

(NRI) will be used for the primary analysis of the primary efficacy variable. These subjects will be defined as non-responders at a specific visit or at all subsequent visits after the time of study discontinuation. In additional sensitivity analyses, an ‘observed cases’ analysis will also be performed (no imputation of missing HiSCR) and subjects who receive specific rescue therapy will also be considered a non-responder from the time that the rescue therapy was taken to the end of the Treatment Period ([Section 8.2.3](#)).

For the hsCRP data, measurements that are below the limit of quantification (BLQ) will be imputed with half of the lower limit of quantification (LLOQ) for the purpose of calculating summary statistics, changes from Baseline and ratio to Baseline.

The handling of any missing data for the other exploratory efficacy data is described or referenced in the respective sections where the analysis of this data is described.

4.2.2 Pharmacodynamic and pharmacokinetic data

For the PD data (cytokines, chemokines, flow cytometry and additional variables as measured), measurements that are BLQ will be imputed with half of the LLOQ for the purpose of calculating summary statistics and changes from Baseline. Measurements that are ALQ, if applicable, will be imputed to the upper quantification limit.

Measurements of PK concentration that are BLQ will be imputed with half of the LLOQ for the purpose of calculating the geometric mean and its 95% CI, the geoCV, the arithmetic mean and SD for the summaries and figures.

For the individual figures, any concentrations that are BLQ will be regarded as missing, with the exception of predose BLQ measurements on Day 1, which will be imputed with zero for linear scale plots.

4.2.3 Safety laboratory data

The rules for handling values that are BLQ or ALQ in the safety laboratory data will be the same as those described for PK data in [Section 4.2.2](#).

4.2.4 Dates

Partial dates may be imputed for the following reasons:

- Classification of AEs as treatment-emergent
- Classification of medications as prior or concomitant

Imputed dates will not be shown in the listings; all dates will be displayed as reported in the database.

The following rules will be applied for partial start dates:

- If only the month and year are specified and the month and year of the first dose of IMP is not the same as the month and year of the start date then the 1st of the month will be used, or the date of Screening if this is later (if the latter imputation results in an end date that is earlier than the start date, then the 1st of the month will be used). If time is missing this will be imputed as 00:00 h
- If only the month and year are specified and the month and year of the first dose of IMP is the same as the month and year of the start date, then the date of the first dose of IMP will be

used. If this results in an imputed start date that is after the specified end date, then the 1st of the month will be used, or the date of Screening if this is later (if the latter imputation results in an end date that is earlier than the start date, then the 1st of the month will be used). If the imputed date is the same as the date of the first dose of IMP then time will be imputed as the start time of the first injection (ie, an AE will be regarded as treatment-emergent and a medication will be classified as concomitant)

- If only the year is specified, and the year of the first dose of IMP is not the same as the year of the start date then January 01 of the year of the start date will be used. If time is missing this will be imputed as 00:00 h
- If only the year is specified, and the year of the first dose of IMP is the same as the year of the start date, then the date of the first dose of IMP will be used. If this results in an imputed start date that is after the specified end date, then January 01 of the year of the start date will be used, or the date of Screening if this is later (if the latter imputation results in an end date that is earlier than the start date, then January 01 will be used). If the imputed date is the same as the date of the first dose of IMP then time will be imputed as the start time of the injection (ie, an AE will be regarded as treatment-emergent and a medication will be classified as concomitant)

The following rules will be applied to partial stop dates:

- If only the month and year are specified, then the last day of the month will be used
- If only the year is specified, then December 31 of the known year will be used
- If the stop date is completely unknown, the stop date will not be imputed

Partially missing dates will be imputed as described above and the duration of each AE will be calculated in days as follows:

$$\text{Duration of AE} = (\text{Date of Outcome} - \text{Date of Onset}) + 1$$

4.3 Handling of repeated and unscheduled measurements

All repeated and unscheduled measurements will be presented in the data listings, where applicable. The following general rules will apply to all repeated and unscheduled measurements:

- For repeated measurements obtained prior to the first dose of IMP the latest value (which may be scheduled or unscheduled) will be used in the calculation of the descriptive statistics
- For repeated measurements obtained at the designated Baseline visit, the latest value (which may be scheduled or unscheduled) will be defined as the Baseline provided that this occurred prior to the first dose of IMP
- For repeated measurements obtained at any time point after the first dose of IMP, the values will not be included in the calculation of descriptive statistics or changes from Baseline.
- Unscheduled measurements performed for the Early Withdrawal (EW) visit will be assigned to the appropriate visit ([Section 4.4](#)) and analyzed accordingly

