8. Subjects with a HADS-D score ≥ 15 must be withdrawn. Any subject who has a HADS-D score of ≥ 10 should be referred immediately to a Mental Healthcare Professional for further evaluation and potential withdrawal by the Investigator.

9. Subject experiences an AE as described below:
- Any Common Terminology Criteria for Adverse Events (CTCAE) Grade 3 and above AE that is assessed as related to study drug in the opinion of the Investigator.
 - If the event is deemed to be not related to study drug by the Investigator, the subject may remain in the study after approval by the Medical Monitor and/or UCB Study Physician.
 - Any CTCAE Grade 2 event that is evaluated as related to study drug in the opinion of the Investigator, is persistent, and falls into any of the following System Organ Classes: “Blood and lymphatic disorders,” “Cardiac disorders,” or “Vascular disorders.”
 - Persistent is defined as lasting 28 days or more, which spans at least 2 bimekizumab dosing visits.

10. Subject has a clinical laboratory value meeting the following criteria:

- CTCAE Grade 3 and above: subject must be withdrawn regardless of relationship to study drug or duration of event, unless the abnormal laboratory value is a natural variation of a condition pre-existing before Baseline (eg, hypercholesterolemia).
- CTCAE Grade 2
 - Subject may remain in the study if the event is transient. If a subject has a Grade 2 laboratory abnormality that is not an expected natural variation of a condition present before Baseline, a retest is required within 1 to 2 weeks at a scheduled or unscheduled visit. If the repeat value is below Grade 2, the subject may receive the next scheduled study treatment. If the value on the repeat is still Grade 2 or above, a second repeat test must be performed and results made available prior to the next scheduled study treatment. If this second repeat value is still Grade 2 or above, the subject must be withdrawn.

11. Subjects with newly diagnosed Inflammatory Bowel Disease (IBD) or with IBD flares during the study must:

- Be referred, as appropriate, to a healthcare professional treating IBD, such as a gastroenterologist
- Discontinue the IMP and be followed-up until resolution of active IBD symptoms

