≥3xULN (and ≥2x Baseline) and <5xULN (and ≥2x Baseline)	<2xULN	No	Discussion with Medical Monitor required. Consider need for hepatology consult if there is no evidence of resolution (see Follow-up requirements). ^c	Further investigation – immediate IMP discontinuation not required (see Section 11.2.1.2). IMP discontinuation required if any of the following occur: 
 • Subject cannot comply with monitoring schedule. • Liver chemistry values continue to increase during 2 week monitoring period. • Liver chemistry values remain ≥3xULN (and ≥2x Baseline) after 2 weeks of monitoring without evidence of resolution. 	Essential: Every attempt must be made to have repeat liver chemistry values and additional testing completed within 48 hours at the site with HCP (see Section 11.2.1.4).	Monitoring of liver chemistry values at least twice per week for 2 weeks. ^d 
 • Immediate IMP discontinuation required if liver chemistry values continue to increase. After 2 weeks of monitoring liver chemistry values: 
 • Discontinue IMP if levels remain ≥3xULN (and ≥2x Baseline) without evidence of resolution.^d Continue to monitor until values normalize, stabilize, or return to within Baseline values. ^d

ALP=alkaline phosphatase; ALT=alanine aminotransferase; ASAP=as soon as possible; AST=aspartate aminotransferase; HCP=healthcare practitioner; IMP=investigational medicinal product; NA=not applicable; PDILI=potential drug induced liver injury; ULN=upper limit of normal

^a Hepatitis symptoms include fatigue, nausea, vomiting, and right upper quadrant pain or tenderness; hypersensitivity symptoms include eosinophilia (>5%), rash, and fever (without clear alternative cause).

^b If the subject also has ≥2xULN ALP, the possibility of an indication of biliary obstruction should be discussed with the Medical Monitor.

^c Details provided in [Section 11.2.1.1](#). The local hepatologist is the expert usually consulted by the treating physician for assessment and management of potential hepatic disease. This would usually be a hepatologist, but may be a gastroenterologist.

^d Unless an alternative monitoring schedule is agreed by the Investigator and UCB responsible physician. Determination of stabilization is at the discretion of the Investigator in consultation with the hepatologist (as applicable) and UCB responsible physician, as needed.

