11.3 Clinical laboratory evaluations

Laboratory data (chemistry, hematology and urinalysis) and changes from Baseline (if applicable) for numeric variables will be listed by treatment group and visit. Any laboratory variables that are BLQ or ALQ will be handled as described in [Section 4.2.3](#). Values outside the

reference range for the numeric variables will be flagged in the listings and in addition, will be listed separately. The reference ranges will also be reported in the listings.

Chemistry and hematology variables presented in [Table 11–1](#) will be summarized by treatment group at each visit, for both observed values and changes from Baseline. Figures of mean and mean change from Baseline will be presented by treatment for the absolute neutrophil count (ANC). All treatment groups will be overlaid on the same plot and the plot will include the error bars based on the SD (ie, mean +/-SD).

Laboratory variables will be grouped according to the laboratory function panel and categorized as normal, high or low, if applicable, based on the reference range supplied by the analytical laboratory. For selected variables that are identified in [Table 11–1](#), the change in category from Baseline will be presented in shift tables for all post-Baseline visits.

The number and percentage of subjects with treatment-emergent markedly abnormal (TEMA) values will be tabulated by treatment group and visit. Markedly abnormal laboratory values will generally be defined as those categorized as Grade 3 or Grade 4 as per the Rheumatology Common Toxicity Criteria (RCTC) Version 2.0 (Woodworth et al, 2007). Communication with the lead author of the RCTC publication has revealed that the reference ranges for absolute lymphocyte counts (ALC) are in error, therefore ALC criteria will follow the ranges defined as per the Common Terminology Criteria for Adverse Events (CTCAE) Version 4.03 (United States Department of Health and Human Services, 2010). Additional laboratory variables (not present in the RCTC publication) will also be categorized as per the CTCAE Version 4.03. The criteria for identifying TEMA values are presented in [Table 14–7](#) and [Table 14–8](#) for hematology and chemistry values respectively.

Laboratory measurements meeting the criteria for TEMA will be listed separately for hematology and chemistry. The listings will include all measurements for any variable with at least 1 TEMA result for each subject

Table 11–1: Laboratory measurements

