14.7 Treatment-emergent abnormal liver values

The criteria for identifying treatment-emergent liver function abnormalities are presented in [Table 14–9](#). Subjects will be counted in all applicable categories for the tabulations ie, a subject with ≥5 x ULN in AST will also be counted in the ≥3 x ULN in AST category, the ≥3 x ULN in AST or ALT category and the ≥5x ULN in AST or ALT category.

Table 14–9: Definition of treatment-emergent liver function values

Criterion
≥3 x ULN increase for AST
≥5 x ULN increase for AST
≥10 x ULN increase for AST
≥20 x ULN increase for AST
≥3 x ULN increase for ALT
≥5 x ULN increase for ALT
≥10 x ULN increase for ALT
≥20 x ULN increase for ALT
≥3 x ULN increase for AST or ALT
≥5 x ULN increase for AST or ALT
≥10 x ULN increase for AST or ALT
≥20 x ULN increase for AST or ALT
≥1 x ULN increase for bilirubin

Table 14–9: Definition of treatment-emergent liver function values

Criterion
≥1.5 x ULN increase for bilirubin
≥1.5 x ULN increase for ALP
≥1 x ULN increase for bilirubin and 3 x ULN increase of either AST or ALT (at the same visit)
≥2 x ULN increase for bilirubin and 3 x ULN increase of either AST or ALT (at the same visit)

ALP=alkaline phosphatase; ALT=alanine aminotransferase; AST=aspartate aminotransferase; ULN=upper limit of normal.

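### By-visit safety abnormality counts have no stated place for values from protocol-mandated retests, so an abnormality or higher grade first found off schedule would be listed but not counted

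*SAP*

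**What the plan says.** SAP 4.3 opens with a broad scope: "The following general rules will apply to all repeated and unscheduled measurements". Its post-dose bullet is narrower: it names repeats only, and bars them from summary statistics and changes from Baseline. It begins: "For repeated measurements obtained at any time point after the first dose of IMP, the values will not be included in the calculation of descriptive". One further bullet deals with a kind of unscheduled value: "Unscheduled measurements performed for the Early Withdrawal (EW) visit will be assigned to the appropriate visit". Other unscheduled post-dose values get no rule beyond appearing in the listings.

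SAP 11.3 sets the laboratory count: "The number and percentage of subjects with treatment-emergent markedly abnormal (TEMA) values will be tabulated by treatment group and visit". SAP 11.4.1 and 11.4.2 do the same for vital signs and QTcF categories, with denominators taken at the specific visit. The liver table in SAP 11.3 and Table 14-9 works differently: it counts subjects who are abnormal at any visit after Baseline.

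The protocol generates off-schedule laboratory values by design. For a Grade 2 laboratory abnormality (Protocol 6.3, criterion 10), "a retest is required within 1 to 2 weeks at a scheduled or unscheduled visit". Protocol 11.2.1 requires abnormal hepatic tests to be repeated. For transaminases from 3 to below 5 times ULN without symptoms, Table 11-3 adds: "Monitoring of liver chemistry values at least twice per week for 2 weeks".

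**The concern.** Leaving repeats out of visit means is sound practice, because it stops subjects who are sampled more often from weighing more heavily. A threshold count has a different purpose: it asks whether a subject ever crossed a limit. Retesting is triggered by an abnormal result, so the values without a stated place in these counts come disproportionately from the subjects with a possible signal.

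Safety is part of the secondary objective. Protocol 11.1.1.4 names cytopenias and liver enzyme changes among the topics for special monitoring. An incidence table that misses abnormalities first seen on retest would understate exactly these topics, and arms of about 20 and 40 leave little room for a missed case.

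**Working it through.** The plan gives no figure on this point, so the check compares the rules and counts sampling times.

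1. **Scheduled draws.** Protocol Table 5-1 places post-dose hematology and biochemistry at Weeks 4, 8, 12 and 30, which is 4 draws. The gaps are 8 − 4 = 4, 12 − 8 = 4 and 30 − 12 = 18 weeks.

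2. **Where a Grade 2 retest falls.** One to two weeks after the Week 4, 8 or 12 draw means Weeks 5–6, 9–10 or 13–14. None of these has a scheduled laboratory draw. The ±3-day visit window does not change this: the latest retest after Week 4 is 28 + 3 + 14 = 45 days after first dose, and the earliest Week 8 draw is 56 − 3 = 53 days. For Weeks 8 and 12 the comparison is 56 + 3 + 14 = 73 against 84 − 3 = 81.

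3. **Liver monitoring.** Twice a week for 2 weeks is at least 2 × 2 = 4 draws. That equals the number of scheduled post-dose draws in the whole study.

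4. **Where such a value can be counted.**

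| Count | Tabulated over | States whether repeats or unscheduled values count | Any-time row |
|---|---|---|---|
| TEMA laboratory (SAP 11.3) | Each visit | No | No |
| TEMA/PCS vital signs (SAP 11.4.1) | Each visit | No | No |
| QTcF categories (SAP 11.4.2) | Each visit | No | No |
| Liver thresholds (Table 14-9) | Any visit after Baseline | No | In effect yes, but its data source is unclear |

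SAP 4.4 points the same way. Early Withdrawal data mapped to a visit at which that assessment is not scheduled are left out of summary statistics and only listed. The one exception is for anti-bimekizumab antibodies, made so that by-visit and overall counts agree. Laboratory data get no such exception.

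5. **Example (the course is assumed, the thresholds are the documents').** A subject has a Grade 2 neutrophil count at Week 4. The retest at Week 5 is below 1.0 x10^9/L, and the count has recovered by Week 12. Protocol 6.3, criterion 6, withdraws the subject from IMP below 1.0 x10^9/L. SAP Table 14-7 sets Grade 3 TEMA at 0.5 to below 1.0. A subject withdrawn from IMP is asked back for Week 12 and the Safety Follow-Up Visit, so Week 8 need not supply a value. The TEMA table then shows nothing for this subject at any visit. The cytopenia table does not fill the gap unless the event was serious, because SAP 14.9.4 admits serious TEAEs only.

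6. **Size per case.** 1/20 = 5 percentage points; 1/40 = 2.5 percentage points.

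7. **Hy's Law row (minor).** SAP 14.9.8 sends Hy's Law cases to the liver table. The closest row there is "≥2 x ULN increase for bilirubin and 3 x ULN increase of either AST or ALT (at the same visit"). Protocol 11.1.1.3 also requires that ALP is not at or above 2 times ULN, and no row in Table 14-9 applies that condition.

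**The case against.** The best reply is that SAP 4.3 was never meant to reach these counts. Its wording is that "the values will not be included in the calculation of descriptive statistics or changes from Baseline", which reads most easily as means and changes. SAP 3.1 has separate reporting rules for percentages and for descriptive statistics, SAP 6.2 contrasts descriptive statistics with categorical summaries, and SAP 11.4.1 treats the two apart. This is a fair reading, but not the only one. Protocol 15.2 introduces counts and percentages under descriptive statistics, and SAP 3.1 uses the term for the overview of safety results. Even on the narrow reading, a table by scheduled visit has no stated place for a Week 5 retest.

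Several stronger inferences are tempting and are not supported:

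- *Every repeated or unscheduled value is dropped.* The bullet names repeats only, and Early Withdrawal values are mapped and can be analysed.
- *The liver counts are biased downward.* Protocol 8.12 defines an Unscheduled Visit at which safety laboratory samples may be taken, so a count over any post-Baseline visit can be read to include it.
- *A subject who triggers a retest disappears from the counts.* The scheduled value still counts if it meets a threshold. ALT of 3.5 times ULN at Week 4 is already Grade 3 TEMA under Table 14-8, and the SAP specifies no separate Grade 4 row.
- *Retesting of vital signs or ECGs is mandated too.* The retest requirements cited here concern laboratory values. For vital signs and QTcF the point is only the missing any-time row.
- *The signals go unreported.* All values are listed, TEMA listings show every measurement of the affected variable, PDILI events must be reported as AEs, and SAP 14.9.8 provides adjudication of PDILI cases.

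The last item reduces the loss but does not restore the incidence. Listings give no rates, and AE tables carry coded terms rather than laboratory thresholds.

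**Conclusion.** The point stands as a gap in the TEMA laboratory count and an ambiguity in the liver table. No text brings retest values into the by-visit counts, and a Grade 2 retest done on time does not coincide with a scheduled draw. Any effect on the TEMA count is downward. It is limited to abnormalities, or higher grades where grades are shown, first found off schedule. Each uncounted subject is worth 2.5 percentage points in the bimekizumab arm and 5 in either other arm.

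This assumes the planned arm sizes and that the programmers follow the SAP as written. The documents give no basis for estimating how many subjects would be affected. The primary efficacy analysis is untouched. The Hy's Law mismatch is minor: the row is broader than the protocol's laboratory definition, and adjudication can correct for that. The change should be made, because the data are already collected and a worst-value rule is the better method for a threshold count.

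**What to change.** - In SAP 4.3, limit the post-dose exclusion to by-visit summary statistics and changes from Baseline, and state that it covers both repeated and unscheduled values.
- In SAP 11.3, 11.4.1 and 11.4.2, add an any-time-post-Baseline row to the TEMA laboratory, PCS vital-sign and QTcF category tables, using each subject's worst value from all scheduled, repeated and unscheduled measurements. Keep the by-visit rows.
- For Table 14-9, state that the count uses the same full set of measurements.
- As a minor addition, give Table 14-9 a row for ALT or AST ≥3xULN with bilirubin ≥2xULN and ALP <2xULN. This matches the laboratory part of the protocol's potential Hy's Law definition. The protocol's requirement of no alternative explanation cannot be read from laboratory values, so keep the adjudication in SAP 14.9.8.

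The cost is a SAP amendment before database lock and a little programming. No new data are needed. Abnormality counts may rise slightly.
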